## PROTOCOL AMENDMENT SUMMARY OF CHANGES TABLE CHANGES

### DOCUMENT HISTORY

Document	Country/countries impacted by amendment	Date, version
Amended Clinical Trial Protocol 04	All	11-Jun-2020, version 1 (electronic 4.0)
Amended Clinical Trial Protocol 03	All	29-Apr-2020, version 1 (electronic 3.0)
Amended Clinical Trial Protocol 02	All	08-Apr-2020, version 1 (electronic 2.0)
Amended Clinical Trial Protocol 01	All	26-Mar-2020, version 1 (electronic 1.0)
Original Protocol	All	18-Mar-2020, version 1 (electronic 1.0)

### Amended protocol [04] (11-Jun-2020)

This amended protocol 04 (amendment 04) is considered to be substantial based on the criteria set forth in Article 10(a) of Directive 2001/20/EC of the European Parliament and the Council of the European Union.

### OVERALL RATIONALE FOR THE AMENDMENT

The main purpose of the amendment is to close enrollment into the sarilumab 200 mg IV arm while maintaining the original 2:1 ratio of sarilumab 400 mg IV to placebo. This amendment also clarifies instructions and provides additional guidance to investigators regarding follow-up and reporting of adverse events of special interest (AESI).

#### Protocol amendment summary of changes table

Section # and Name	Description of Change	Brief Rationale
Section 1.1 Synopsis, Section 1.2 Schema, Section 2.1 Study Rationale, Section 4.1 Overall Design, Section 4.2 Scientific Rationale for Study Design, Section 4.3 Justification for Dose, Section 6.1. Study Interventions administered (Table 3)	Closed enrollment to the sarilumab 200 mg IV arm	Based on anticipation of a more favorable benefit-risk profile in the 400 mg arm versus the 200 mg arm, enrollment in the 200 mg arm will be closed upon implementation of amended protocol 04.

Section # and Name	Description of Change	Brief Rationale
Section 1.3 Schedule of Activities	Urinalysis and urine culture results, serum IL-6, adverse events	The timing of urinalysis, urine culture results, serum IL-6, and adverse events assessments was clarified. No changes were made to the collection schedule.
Section 5.2	E04 was modified to clarify that oral corticosteroids were a type of systemic corticosteroids.	Clarification of definition.
Section 10.3.1 Definition of AE	Events meeting the AE definition: Removed: "Lack of efficacy" or "failure of expected pharmacological action" per se will not be reported as an AE or SAE. Such instances will be captured in the efficacy assessments. However, the signs, symptoms, and/or clinical sequelae resulting from lack of efficacy will be reported as AE or SAE if they fulfil the definition of an AE or SAE.	This bullet is duplicated in error. The same information is included in the first bullet.
Section 10.3.1 Definition of AE	Events meeting the AE definition: The signs, symptoms, and/or clinical sequelae resulting from lack of efficacy will be reported as AE or SAE if they fulfil the definition of an AE or SAE. Also, "lack of efficacy" or "failure of expected pharmacological action" also constitutes an AE or SAE.	This bullet is contradictory to the information provided, stating "Lack of efficacy" or "failure of expected pharmacological action" per se will not be reported as an AE or SAE.
Section 10.3.2.1 Recording and follow-up of AE and/or SAE	Added tables for assessment of intensity for infusion related reactions, hypersensitivity reactions, and neutropenia. Added guidance for the follow-up of AESIs of ALT increase and Grade 4 Neutropenia.	Provide guidance to the investigator.

# 1 PROTOCOL SUMMARY

## 1.1 SYNOPSIS

**Protocol title:** An Adaptive Phase 3, Randomized, Double-Blind, Placebo-Controlled Study Assessing Efficacy and Safety of Sarilumab for Hospitalized Patients with COVID-19

**Short title:** Sarilumab COVID-19

**Rationale:** See [Section 2.1](#)

## Objectives and endpoints

---

### Objectives

---

#### Primary

- To evaluate the clinical efficacy of sarilumab relative to the control arm in adult patients hospitalized with severe or critical COVID-19

---

#### Secondary

- Evaluate the 28-day survival rate
- Evaluate the clinical efficacy of sarilumab compared to the control arm by clinical severity
- Evaluate changes in the National Early Warning Score 2 (NEWS2)
- Evaluate the duration of predefined symptoms and signs (if applicable)
- Evaluate the duration of supplemental oxygen dependency (if applicable)
- Evaluate the incidence of new mechanical ventilation use during the study
- Evaluate the duration of new mechanical ventilation use during the Study
- Evaluate the proportion of patients requiring rescue medication during the 28-day period
- Evaluate need for admission into intensive care unit (ICU)
- Evaluate duration of hospitalization (days)
- The safety objectives of the study are to evaluate the safety of sarilumab through hospitalization (up to day 29 if patient is still hospitalized) compared to the control arm as assessed by incidence of:
  - Serious adverse events (SAEs)
  - Major or opportunistic bacterial or fungal infections in patients with grade 4 neutropenia
  - Grade  $\geq 2$  infusion related reactions
  - Grade  $\geq 2$  hypersensitivity reactions
  - Increase in alanine transaminase (ALT)  $\geq 3X$  ULN (for patients with normal baseline) or  $>3X$  ULN AND at least 2-fold increase from baseline value (for patients with abnormal baseline)
  - Major or opportunistic bacterial or fungal infections

---

---

### **Tertiary/exploratory**

- Evaluate the virologic changes in the treatment arms compared to the control arm as assessed by nasopharyngeal (NP) and blood quantitative SARS-CoV-2 counts
- To evaluate the cytokine profile and additional biomarkers that may be associated with efficacy and safety associated with sarilumab treatment
- To evaluate the incidence of new or worsening laboratory-confirmed serious secondary infections in the treatment arms as compared to the control arm
- To characterize the concentrations of sarilumab in serum over time
- Patients will not be recalled after discharge for any missing exploratory assessments.

---

### **Overall design:**

This study is an adaptive, multi-national, multi-center, phase 3, randomized, double-blind, placebo-controlled trial to evaluate the efficacy and safety of sarilumab in hospitalized adults with severe or critical COVID-19. Patients were randomized in a 2:2:1 ratio to sarilumab 400 mg intravenous (IV), 200 mg IV, or matching placebo IV in a stratified manner prior to Amended Protocol 04. The sarilumab 200 mg IV dose arm will be closed for patients enrolled after Amended Protocol 04 is implemented.

Patients will receive a single dose of study drug on Day 1. Patients may receive a second dose with study drug (based on the original treatment group assigned) 24 to 48 hours after the first dose, if they meet prespecified criteria (see [Section 4.1](#)). Randomization will be stratified by severity of illness (severe OR critical) and use of systemic corticosteroids (Yes OR No).

**Study duration:** An individual patient will complete the study approximately 60 days from screening to follow-up on day  $60 \pm 7$  days. Patients will not be required to return to the hospital once discharged.

**End of study definition:** The end of study (EOS) is defined as the date the last patient completes the last study assessment (in the hospital or via a follow-up phone call if the patient was discharged from the hospital before day 60), withdraws from the study, or is lost to follow-up (ie, the study patient can no longer be contacted by the investigator).

**Population:** Hospitalized adult ( $\geq 18$  years old) male and female patients with COVID-19.

**Disclosure Statement:** This is a parallel group treatment study with 3 arms that is participant and Investigator blinded.

### **Number of participants:**

Approximately 400 patients randomized and treated with study medication.

## **Intervention groups and duration:**

### Study intervention(s)

Participants who satisfy the inclusion and exclusion criteria will be randomized (2:2:1) to one of the following IMP treatment groups:

- Sarilumab 400 mg IV
- Sarilumab 200 mg IV
- Matching placebo IV

### *Investigational medicinal product(s)*

- Formulation: a 175 mg/ml sarilumab solution in a pre-filled syringe to deliver 200 mg in a 1.14 ml solution
- Route of administration: intravenous (IV)
- Dose regimen:
  - One infusion of sarilumab 400 mg IV, (two sarilumab 200 mg, single dose prefilled syringes (PFS), mixed in [REDACTED] 0.9% sodium chloride solution for IV use)
  - One infusion of sarilumab 200 mg IV, (one sarilumab, single dose PFS, mixed in [REDACTED] 0.9% sodium chloride solution for IV use)
  - One infusion of matching placebo [REDACTED] 0.9% sodium chloride solution for IV use).

For each treatment group, patients will receive a single dose of study drug on Day 1. Patients may receive a second dose with study drug (based on the original treatment group assigned) 24 to 48 hours after the first dose, if they meet prespecified criteria (see [Section 4.1](#)).

## **Statistical considerations:**

### **Primary endpoint:**

The primary endpoint is the time to improvement of 2 points in clinical status assessment from baseline using the 7-point ordinal scale.

The 7-point ordinal scale is an assessment of the clinical status. The scale is as follows:

1. Death;
2. Hospitalized, on invasive mechanical ventilation or extracorporeal membrane oxygenation (ECMO);
3. Hospitalized, on non-invasive ventilation or high flow oxygen devices;
4. Hospitalized, requiring supplemental oxygen;
5. Hospitalized, not requiring supplemental oxygen - requiring ongoing medical care (COVID-19 related or otherwise);

6. Hospitalized, not requiring supplemental oxygen - no longer requires ongoing medical care
7. Not hospitalized

**Secondary endpoints:**

**Key secondary endpoint:**

- Percent of patients alive at Day 29

**The other secondary efficacy endpoints are:**

- Proportion of patients with one point improvement from baseline in clinical status assessment at days 4, 7, 15, 21, 29 using the 7-point ordinal scale
- Mean change in the 7-point ordinal scale from baseline to days 4, 7, 15, 21, 29 (or until discharge)
- Time to resolution of fever defined as body temperature ( $\leq 36.6^{\circ}\text{C}$  [axilla], or  $\leq 37.2^{\circ}\text{C}$  [oral], or  $\leq 37.8^{\circ}\text{C}$  [rectal or tympanic]) for at least 48 hours without antipyretics or until discharge, whichever is sooner,
- Time to resolution of fever (as defined above) and improvement in oxygenation (as defined below)
- Days with fever ( $> 37.4^{\circ}\text{C}$  [axilla], or  $> 38.0^{\circ}\text{C}$  [oral], or  $> 38.4^{\circ}\text{C}$  [rectal or tympanic]) based on maximum value observed during a 24-hour period
- Time to change in National Early Warning Score 2 (NEWS2) from baseline
- Time to NEWS2 of  $< 2$  and maintained for 24 hours
- Mean change from baseline to days 4, 7, 15, 21, 29 in NEWS2
- Time-to-improvement in oxygenation ( $[\text{SpO}_2]/[\text{FiO}_2]$  of 50 or greater) compared to the nadir for at least 48 hours, or until discharge, whichever is sooner
- Alive off supplemental oxygen at day 29
- Days of hypoxemia ( $\text{SpO}_2 < 93\%$  on room air, or requiring supplemental oxygen, or mechanical ventilatory support)
- Days of supplemental oxygen use
- Days of resting respiratory rate  $> 24$  breaths/min (maximum value if recorded at more than once a day)
- Time to oxygen saturation  $\geq 94\%$  on room air
- Ventilator free days in the first 28 days (to day 29)
- Initiation of mechanical ventilation, non-invasive ventilation, or use of high flow nasal cannula (for those not requiring these interventions at baseline)
- Proportion of patients requiring rescue medication during the 28-day period

- ICU status (among those not in an ICU at baseline, record if transferred to the ICU or the need to transfer to the ICU [if the ICU is not available])
- Days of hospitalization among survivors

## Safety

The secondary safety endpoints are:

- Incidence of serious adverse events
- The incidence of major or opportunistic bacterial or fungal infections
- The incidence of major or opportunistic bacterial or fungal infections in patients with grade 4 neutropenia
- The incidence of hypersensitivity reactions, infusion reactions, gastrointestinal perforation
- White blood cell count, hemoglobin, platelets, creatinine, total bilirubin, alanine aminotransferase (ALT) on days 1, 4, 7, 15, 21, 29 (if still hospitalized)

## Procedures and assessments

Efficacy procedures and assessments include clinical data collection, body temperature, oxygen delivery and oxygenation, resting SpO2, and National Early Warning Score2.

Safety procedures and assessments include laboratory testing, vital signs, targeted physical examination, and concomitant medication review.

## Statistical plan

Assuming that accrual duration is 3 months (~90 days) with each patient followed for a period of at least 29 days, the proportions of patients with two points improvement from baseline in clinical status assessment at day 15 are 45% and 70% for placebo and sarilumab, respectively, a total sample size of approximately 400 patients with a 2:2:1 randomization ratio provides at least 90% power for pairwise comparisons between each sarilumab dose (400 mg IV or 200 mg IV; n~160 each) and placebo (n~80), using a log-rank test for superiority at a two-sided significance level of 0.05. Sample size calculation was performed using PASS 14.

The primary analysis is planned when the last patient randomized reaches Day 29 (or planned Day 29 if the patient is discharged or leaves the study early). Final analysis will be performed at study end at Day 60.

The primary endpoint, which is the time to improvement of 2 points in clinical status assessment from baseline using the 7-point ordinal scale, will be analyzed using a log-rank test stratified by randomization stratum with treatment as a fixed factor in the mITT population. P-value for the pairwise treatment comparison versus placebo will be provided. Estimation of treatment effect of each sarilumab dose will be provided as hazard ratio (sarilumab versus placebo) using Cox proportional hazards model stratified by the randomization stratum with treatment as a covariate,

along with 2-sided confidence intervals. Kaplan-Meier (KM) plot and the median time-to-improvement of 2 points will also be provided.

The key secondary endpoint, which is percent of patients alive at Day 29, will be analyzed using a Cochran-Mantel-Haenszel (CMH) test stratified by randomization stratum in the mITT population. Estimation of treatment effect of each sarilumab dose will be reported as difference in proportion of patients alive at Day 29 (sarilumab - placebo), along with 95% confidence levels. P-value for the pairwise treatment comparison versus placebo will be provided.

For the primary and key secondary endpoints, multiplicity will be controlled via a hierarchical testing procedure in the following order:

1. Primary endpoint sarilumab 400 mg versus placebo
2. Key secondary endpoint sarilumab 400 mg versus placebo
3. Primary endpoint sarilumab 200 mg versus placebo
4. Key secondary endpoint sarilumab 200 mg versus placebo

If one sarilumab dose is discontinued for safety reasons, then all comparisons versus placebo for that dose will be removed and the remaining comparisons will be tested in the order specified above.

An interim analysis is planned to be performed when approximately 50% of total planned number of patients (~200) are randomized. The purpose of the interim analyses is to obtain an understanding of the possible drug effect in the population under study. An administrative alpha of 0.001 will be spent at interim analysis (1).

[figure not shown]
The interim analyses will be performed by an external statistical analysis center and are separated from personnel involved in the trial conduct. The unblinded results can only be viewed by a small group of senior sponsor individuals, who are separate from sponsor personnel involved in the conduct of the study. People involved in the conduct of the study (Patients, Investigators, Study Team, and Project Team) will have no access to the interim analysis results.

#### **Independent Data Monitoring Committee: Yes**

An independent data monitoring committee (IDMC) is established to oversee the welfare of patients in the study and to monitor all data to make recommendations to continue the study, to modify the protocol, or to terminate the study. The IDMC members include 2 to 4 independent expert physicians with relevant medical specialist training and 1 statistician.

## 1.2 SCHEMA

**Figure 1 - Graphical study design**

\* If the patient has been discharged from the hospital before Day 29, the study site staff will contact the patient for a follow-up phone call

\*\* The EOS will be on Day 60 or day of death, whichever comes first. If the patient has been discharged from the hospital before Day 60, the study site staff will contact the patient for a follow-up phone call

\*\*\* Enrollment closed upon implementation of Amended Protocol 04

R: Randomized; EOS: End of study; IV: intravenous; N: number

### 1.3 SCHEDULE OF ACTIVITIES (SOA)

Study Procedure	Screening Visit 	Baseline Visit 	Follow-up Until Hospital Discharge							EO S 	Discharge Before Day 29 
			2 or 3	4	7	15	21	29 	60		
Day	-1 or 1	1									
Window (day)										±7	
Screening/Baseline:											
Inclusion/Exclusion For a positive SARS-CoV-2 test qualification, see footnote 		X									
Informed Consent	X										
Pharmagenomics Sub-Study Consent	X										
Demographics and Medical History	X										
History of hypercapnic respiratory failure 	X										
Randomization		X									
Treatment:											
Study Drug Administration			X	X 							
Assessments:											
Efficacy											
Body Temperature 	X (4 times a day)		Day 1-3: 4 times a day, Day 4-29: 2 times a day							X	
Oxygen Delivery and Oxygenation 	X (4 times a day)		Day 1-3: 4 times a day Day 4-29: record results as assessed							X	
Resting SpO2 	X (4 times a day)		Day 1-3: 4 times a day Day 4-29: record results as assessed							X	
Clinical Daily Assessment (including 7-point ordinal scale) 	X		Daily until discharge							X	
Vital Status (and cause of death)			Daily until discharge						X	X	
Arterial blood gas results (as available) 			X								
Vital Signs  (other than temperature and SpO2)	X		Daily until discharge							X	
Targeted physical examination	X										

Study Procedure	Screening Visit 	Baseline Visit 	Follow-up Until Hospital Discharge							EO S 	Discharge Before Day 29 
			2 or 3	4	7	15	21	29 			
Day	-1 or 1	1							60		
Window (day)									±7		
Optional Electrocardiogram (ECG) 	X										
Record Concomitant Therapy 	X										X
Adverse Events 	X									X	X
Pregnancy Test (WOCBP) 	X										
Bacterial infection testing and fungal infection testing (blood)					X	X					
Laboratory Testing Standard-of-Care (Local Laboratories):											
Hematology Results 	X	X 	X 	X	X	X	X	X			X
Blood Chemistry Results 	X	X 	X 	X	X	X	X	X			X
Urinalysis 	X					X					
Urine Culture Results (if available) 	X					X					
Optional nasopharyngeal swab for SARS-CoV-2 detection 		X			X	X	X	X			X
PK/Biomarkers (Central Laboratories):											
Serum for PK/Sarilumab Concentration 		X 	X 	X 	X	X	X	X 			X 
ADA		X				X 		X			X
Serum IL-6 		X		X	X	X	X	X			X
Serum sIL-6R 		X 						X			X
Blood for PCR SARS-CoV-2  (Not for determining the inclusion criteria)		X		X	X	X	X	X			X
Pharmacogenomics (optional genomic study):											
Blood for DNA/RNA 		X									

ESO: end of study, SpO2: oxygen saturation, CT-scan: computed tomography ECG: electrocardiogram, WOCBP: women of childbearing potential, PK: pharmacokinetic, ADA: antidrug antibodies, sIL-6R: soluble interleukin 6 receptor, IL: interleukin, PCR: polymerase chain reaction, SARS-CoV-2: Severe acute respiratory syndrome coronavirus 2, DNA: deoxyribonucleic acid, RNA: ribonucleic acid, SAE: serious adverse event, AESI: adverse event of special interest.

1. Laboratory-confirmed SARS-CoV-2 infection (eg by PCR), or other commercial or public health assay in any specimen within 2 weeks prior to randomization and no alternative explanation for current clinical condition is required for inclusion.
2. Screening and baseline may occur within 24 hours. Assessments that are noted for both visits should only be assessed once if the baseline visit is within 24 hours of the screening visit. All baseline samples, if obtained, should be collected before study drug administration at baseline visit except post-infusion PK and sIL-6R samples.
3. Patients will have an end of study (EOS) assessment to collect data on survival, adverse events, and history of hospital re-admission. This assessment may be performed by phone. This visit may be performed earlier if a patient withdraws from the study.
4. Patients discharged prior to Day 29 will have a follow-up phone call on Day 29 to collect data on all adverse events, and history of hospital re-admission.
5. Patients discharged prior to Day 29 should have a sample collected on or before day of discharge. Any sample collected within 24 hours of the day of discharge do not need to be repeated.
6. Patients may receive a second dose with study drug 24 to 48 hours after the first dose, if the patient meets prespecified criteria in [Section 4.1](#). Day 2 or 3 samples are only taken from patients who are administered a second dose of study treatment. They should be drawn prior to administration of the second dose of study drug to aid in benefit/risk assessment.
7. Sites are required to capture the history of chronic hypercapnic respiratory failure.
8. Body temperature is described in [Section 8.1.2](#) (up to 4 times a day at screening). Retrospective temperature within the previous 24 hours can be considered for screening. Body temperature to be reported in the CRF should be the maximum value observed during any time period or window ([Section 8.1.2](#)).
9. Oxygen delivery and oxygenation: refer to [Section 8.1.2](#) of the protocol for details (up to 4 times a day at screening). Retrospective readings within the previous 24 hours can be considered for screening.
10. Must be measured after 5 minutes of rest (sitting or supine), and must be measured simultaneously with oxygen delivery and ventilation data.
11. Clinical Data Assessments (including 7-point ordinal scale, status of intubation, Intensive care unit admission/discharge, CT scan, X-rays, and any other imaging performed during hospitalization, daily consciousness for NEWS2 scoring system [2]): refer to [Section 8.1.1](#) of the protocol for details.
12. Results as reported to be recorded in arterial blood gas results electronic case report form (CRF) (as available).
13. Vital signs include height (screening only), weight (screening only), blood pressure, pulse, and respiration rate, See [Section 8.2.1](#)
14. The ECG is optional. Historical ECG from current hospital admission is acceptable.
15. Concomitant therapy: refer to [Section 6.5](#) of the protocol for details.
16. Adverse events: All AEs will be recorded in CRF. Note: any abnormal physical findings requiring medical or surgical intervention must be recorded as an AE.
17. Pregnancy testing to be performed locally in women of childbearing potential (WOCBP) only. Serum or urine pregnancy test are both acceptable.
18. Hematology: refer to [Table 11](#) for details.
19. Blood Chemistry: refer to [Table 11](#) for details.
20. Urinalysis is performed at screening (if feasible) and should be collected one additional time (optional) during the treatment period.
21. SARS-CoV-2 detection will be performed locally. This test is optional.
22. Sarilumab concentration
  - Day 1 sampling: 2 samples with one taken pre dose, and 1 taken within 30 min after the end of infusion; end of infusion sample should be collected from the arm contralateral to that used for IV infusion

- For patients administered a 2nd dose, Day 2 or Day 3 sampling is performed with 2 samples taken on the day of the 2nd dose, with 1 taken pre dose, and 1 taken within 30 min after the end of infusion; end of infusion sample should be collected from the arm contralateral to that used for IV infusion
- Day 4 (approximately 72 hours post first dose)
- The Day 29 or Early Discharge PK sample may be used for ADA analysis

23. In the event of any SAE of severe infusion reaction, or any AESI of anaphylactic reaction or systemic allergic reaction that is related to IMP, ADA samples will be collected at or near the onset of the event for any additional analysis.

24. Serum IL-6 samples must be taken pre-dose. Samples are mandatory for baseline/Day 1, Discharge before Day 29 and Day 29. It is optional on Day 4, 7, 15, and 21.

25. Serum sIL-6R:

- Day 1 sample taken pre dose (as close to initiation of treatment as reasonable)

26. Blood collected will be shipped for the central analysis of SARS-CoV-2 viral load and is not for determining the inclusion criteria.

27. Separate consent is required for participation in the optional genomic sub-study and collection of a blood sample for (DNA/RNA). The sample for genomic DNA/RNA should be collected on Day 1 or may be collected at any visit.

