2.1.5 Pharmacokinetics variables

Sarilumab concentration will be collected at Day 1, 2 or 3 (only for patients with second dose), Day 4, 7, 15, 21 and 29 or early discharge.

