2.4.6 Analysis of pharmacokinetics

Analysis of drug concentration data:

The concentrations of sarilumab over time and pharmacokinetic parameters, as appropriate, will be summarized using descriptive statistics by treatment group and number of sarilumab doses using the PK population.

No formal statistical hypothesis testing will be performed.

2.4.7 Analysis of Pharmacodynamic and Exploratory Biomarker Data:

The concentrations of CRP, IL-6, and sIL-6R over time will be summarized using descriptive statistics by treatment group using the safety population. The analysis will include:

- Observed value, change from baseline and percent change from baseline by each sampling point through Day 29 /EoS.
- The figures of mean \pm standard error (SE) versus scheduled sampling time points.

In addition, ANC will be analyzed similarly.

As an exploratory analysis, the percentage of patients with SARS-CoV-2 positive (either nasopharyngeal swab or PCR) over time will be summarized using the safety population.

The relationship between d-dimer, ferritin, LDH, IL-6, neutrophil:lymphocyte ratio and the clinical assessment using the 7-point ordinal scale will be explored.

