Appendix B Visit windows based on day ranges

Table 4 – Time window for lab summaries

Visit Label	Target Day	Hematology, Chemistry	Bacterial infection testing
Daily follow-up until hospital discharge or Day 29			
Baseline	1	≤1	
Day 4	4	2-5	
Day 7	7	6-10	2-10
Day 15	15	11-17	≥11
Day 21	21	18-24	
Day 29	29	≥25	

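### The schedule's footnotes conflict on when the only baseline sIL-6R sample is drawn, the SAP gives discharge biomarker and PK samples no time point, and it analyzes LDH, which is not a required test

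*Protocol*

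**What the plan says.** **Baseline sIL-6R.** In the protocol's Schedule of Activities (section 1.3), the row "Serum sIL-6R 25" is marked at baseline, at Day 29 and at discharge before Day 29, and nowhere else. Footnote 2 says that baseline samples "should be collected before study drug administration at baseline visit except post-infusion PK and sIL-6R samples". Footnote 25 says of sIL-6R: "Day 1 sample taken pre dose (as close to initiation of treatment as reasonable". SAP 2.1.1 takes as baseline the last value before the first dose.

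**Last sample.** Footnote 5 states: "Patients discharged prior to Day 29 should have a sample collected on or before day of discharge". Its study day therefore varies from patient to patient. For IL-6, footnote 24 says "Samples are mandatory for baseline/Day 1, Discharge before Day 29 and Day 29"; Days 4, 7, 15 and 21 are optional. SAP 2.1.6 refers to the protocol schedule for IL-6 and sIL-6R. SAP 2.4.7 summarizes value, change and percent change at each sampling point up to Day 29/EoS and plots means against scheduled times. For sarilumab concentration, SAP 2.1.5 lists collection at "Day 4, 7, 15, 21 and 29 or early discharge". SAP Appendix B, titled "Time window for lab summaries", has columns only for hematology/chemistry and for bacterial infection testing.

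**LDH.** SAP 2.4.7 will explore "The relationship between d-dimer, ferritin, LDH, IL-6, neutrophil:lymphocyte ratio and the clinical assessment" on the 7-point scale. LDH is in neither protocol Table 11 nor SAP 2.1.4.3.

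**The concern.** The Day 1 sIL-6R sample cannot be replaced. Protocol 2.2 says that sarilumab lowers free sIL-6R, so a sample drawn after infusion may already carry drug effect, and under SAP 2.1.1 it is not a baseline. That patient then has no change score. The value has its own interest too: protocol 4.3 says that sIL-6R levels in COVID-19 are not known in detail and may far exceed those in rheumatoid arthritis.

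The last sample is the only post-dose sIL-6R value and the only mandatory post-dose IL-6 value. If it is shown as a discharge time point, or merged with Day 29, one mean covers different days since dosing. If sarilumab shortens the hospital stay, the mix of days differs by arm, and part of any difference between arms reflects timing rather than drug effect.

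LDH would be available only where someone chose to order it, so the exploratory analysis would rest on a clinically selected subset.

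**Working it through.** There is no figure in the plan to reproduce. The check sets the texts side by side and then illustrates the timing.

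**1. Footnotes 2 and 25.** Footnote 2 can be read in two ways.
- sIL-6R is exempt from pre-dose collection. This contradicts footnote 25.
- The exemption covers a post-infusion sIL-6R sample. None is scheduled: footnote 22 lists an end-of-infusion sample for PK, and footnote 25 lists only a pre-dose sIL-6R sample.

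Either way one footnote is wrong or incomplete. The documents do not say how often a sample would be drawn late. If a share *f* of baselines were lost at random, the standard error of the mean change would rise by 1/√(1 − *f*). For an assumed *f* of 10% to 30%, that is 1/√0.9 = 1.05 to 1/√0.7 = 1.20.

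**2. Where a discharge sample goes.** Take a discharge on Day 6.

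| Measurement | Rule | Placed at |
|---|---|---|
| CRP (chemistry panel, Table 11) | Appendix B, Days 6–10 | Day 7 |
| IL-6, sIL-6R | none | undefined |
| Sarilumab concentration, ADA | none | undefined |

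SAP 2.1.4.3 also lists hematology and chemistry collection as Day 29 or discharge, and there Appendix B settles the mapping. CRP, IL-6 and sIL-6R belong to the same SAP 2.4.7 analysis, yet only CRP has a rule. The label Day 29/EoS does not help: end of study is Day 60 or death, and no biomarker sample is scheduled at Day 60.

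**3. Timing by arm (illustration).** Inputs: 2-point improvement by Day 15 in 70% (sarilumab) and 45% (placebo), from protocol 9.2. Assumptions: constant hazard, and improvement stands in for discharge.

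- Hazard: h = −ln(1 − p)/15. Sarilumab −ln(0.30)/15 = 0.0803 per day; placebo −ln(0.55)/15 = 0.0399 per day.
- Share with a discharge sample before Day 29: 1 − exp(−28h) = 0.89 and 0.67.
- Mean last-sample day if merged with Day 29: 1 + (1 − exp(−28h))/h = 12.1 and 17.9, a gap of 5.7 days.
- Mean day if kept as a separate discharge point: 1 + 1/h − 28·exp(−28h)/(1 − exp(−28h)) = 10.2 and 12.4, a gap of 2.3 days.

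Halving both hazards, to allow for discharge later than improvement, gives merged means of 17.8 and 22.5, a gap of 4.6 days.

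These gaps concern IL-6 and sIL-6R. Placebo patients have no sarilumab concentration to compare, and the plan assumes the same 70% for both doses. For PK the issue is therefore mixed days within a dose group. The documents give no half-life, so I put no figure on it.

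**4. LDH.** Table 11 and SAP 2.1.4.3 both list ferritin and D-dimer, which SAP 2.4.7 analyzes alongside LDH. Neither lists LDH. Protocol 10.2 allows additional tests at the investigator's discretion, so some results may exist, but not on a schedule.

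**The case against.** A reader might infer that the SAP pools sIL-6R discharge samples with Day 29. It does not say so. The phrase joining Day 29 and early discharge is a collection list for sarilumab concentration in SAP 2.1.5. The schedule keeps Day 29 and discharge in separate columns, and SAP 2.4.7 works by sampling point. What stands is that the mapping is undefined, and pooling is neither stated nor excluded.

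A reader might also infer that the sIL-6R change from baseline cannot be interpreted at all. That goes too far. Footnote 25 is the specific rule and requires a pre-dose sample, the SAP's baseline rule excludes post-dose values, and there is a concurrent placebo arm. Day 29 samples have a clear time, although they come from patients still in hospital. The placebo arm does not, however, remove a difference in sampling day between arms.

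The timing figures lean to the high side. A move from 2 to 4 or from 4 to 6 on the scale leaves the patient in hospital, and deaths are ignored.

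The PK objective does not rest on the last sample. Concentration is also measured on Day 1 and on Days 4, 7, 15 and 21, and the named parameters in protocol Table 8 are Cmax and tmax.

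Finally, simply extending the Appendix B ranges to all PK samples would do harm: the Day 2 or 3 samples around a second dose would fall in the Day 4 range (Days 2–5). That objection stands, and the fix allows for it.

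**Conclusion.** Three specific defects hold. Footnotes 2 and 25 must be reconciled on the patient's only baseline sIL-6R sample. The SAP does not say where discharge samples for IL-6, sIL-6R, sarilumab concentration and ADA belong, although it settles the same question for hematology and chemistry. LDH is analyzed without being scheduled.

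The gap in sampling day between arms would be about 6 days if discharge samples were merged with Day 29, and about 2 days if they were kept as a discharge point. Both figures assume a constant hazard, the design rates, and improvement as a proxy for discharge; they are upper-end illustrations and do not describe what the SAP states it will do. The loss of baselines cannot be sized from the documents.

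The affected analyses are descriptive or exploratory. No primary, key secondary or safety conclusion changes. The point is minor, but nearly free to correct.

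**What to change.** **(a) Protocol 1.3.** Remove sIL-6R from the exception in footnote 2 so that it agrees with footnote 25. If a post-infusion sIL-6R sample is intended, schedule it as an additional sample.

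**(b) SAP 2.4.7 and Appendix B.**
- Assign discharge samples for IL-6, sIL-6R, ADA and sarilumab concentration by actual study day, using the existing ranges (2–5, 6–10, 11–17, 18–24, 25 and later).
- Keep nominal times for scheduled PK samples, so that the pre-dose and end-of-infusion samples around a second dose on Day 2 or 3 are not mapped to Day 4.
- Replace Day 29/EoS with a defined last time point.
- Note in the sIL-6R tables that windows before Day 29 contain only discharged patients. Assignment by day aligns time since dosing but does not remove this selection.

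**(c) LDH.** Add it to protocol Table 11 and SAP 2.1.4.3, or remove it from SAP 2.4.7. Adding it cannot recover baselines for patients already enrolled, and protocol 4.3 shows that the interim review has already taken place.

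**Cost.** Part (a) is a footnote edit. Part (b) is SAP text, with no new samples but smaller cells per window. Part (c) is either a deletion or one more analyte on the local panel.
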